7. Subject has received and completed the last 2 infusions without a drug-related adverse event resulting in dose interruption
8. Subject must be able to walk between 200 and 500 meters on the 6MWT
9. Upright FVC must be 30% to 80% of predicted normal value

Exclusion Criteria

1. Subject has received any investigational therapy including adjunctive therapy for Pompe disease, other than alglucosidase alfa within 30 days or 5 half-lives of the therapy or treatment, whichever is longer, prior to the Baseline Visit, or anticipates doing so during the study
2. Subject has received treatment with prohibited medications within 30 days of the Baseline Visit
3. Subject, if female, is pregnant or breastfeeding at screening
4. Subject, whether male or female, is planning to conceive a child during the study
5. Subject requires invasive ventilatory support
6. Subject uses noninvasive ventilatory support \geq 6 hours a day while awake
7. Subject has a medical or any other extenuating condition or circumstance that may, in the opinion of the investigator or the Medical Monitor, pose an undue safety risk to the subject or compromise his/her ability to comply with protocol requirements
8. Subject has a history of anaphylaxis to alglucosidase alfa
9. Subject has a history of high sustained anti-rhGAA antibodies
10. Subject has a history of allergy or sensitivity to miglustat or other iminosugars

11. Subjects with active systemic autoimmune disease such as lupus, scleroderma, or rheumatoid arthritis; all subjects with autoimmune disease must be discussed with the Amicus Medical Monitor
12. Subjects with active bronchial asthma; all subjects with bronchial asthma must be discussed with the Amicus Medical Monitor

Cohort 2

Inclusion Criteria

10. Male and female subjects between 18 and 65 years of age, inclusive
11. Subject must provide signed informed consent prior to any study-related procedures
12. Subjects of childbearing potential must agree to use medically accepted methods of contraception during the study and for 90 days after last co-administration of ATB200 and AT2221
13. Subject has a diagnosis of Pompe disease based on documented deficiency of GAA enzyme activity or by *GAA* genotyping
14. Subject has received ERT with alglucosidase alfa (Myozyme/Lumizyme) for \geq 2 years
15. Subject is currently receiving alglucosidase alfa (Myozyme/Lumizyme), at a regular or set frequency
16. Subject has received and completed the last 2 infusions without a drug-related adverse event resulting in dose interruption
17. Subject must be wheelchair-bound and unable to walk unassisted

Exclusion Criteria

13. Subject has received any investigational therapy, including adjunctive therapy for Pompe disease, other than alglucosidase alfa within 30 days or 5 half-lives of the therapy or treatment, whichever is longer, prior to the Baseline Visit, or anticipates to do so during the study
14. Subject has received treatment with prohibited medications within 30 days of the Baseline Visit
15. Subject, if female, is pregnant or breastfeeding at screening
16. Subject, whether male or female, is planning to conceive a child during the study
17. Subject has a medical or any other extenuating condition or circumstance that may, in the opinion of the investigator or the Medical Monitor, pose an undue safety risk to the subject or compromise his/her ability to comply with protocol requirements
18. Subject has a history of anaphylaxis to alglucosidase alfa
19. Subject has a history of high sustained anti-rhGAA antibodies
20. Subject has a history of allergy or sensitivity to miglustat or other iminosugars

21. Subjects with active systemic autoimmune disease such as lupus, scleroderma, or rheumatoid arthritis; all subjects with autoimmune disease must be discussed with the Amicus Medical Monitor
22. Subjects with active bronchial asthma; all subjects with bronchial asthma must be discussed with the Amicus Medical Monitor

Cohort 3

Inclusion Criteria

18. Male and female subjects between 18 and 65 years of age, inclusive
19. Subject must provide signed informed consent prior to any study-related procedures
20. Subjects of childbearing potential must agree to use medically accepted methods of contraception during the study and for 90 days after last co-administration of ATB200 and AT2221
21. Subject has a diagnosis of Pompe disease based on documented deficiency of GAA enzyme activity or by *GAA* genotyping
22. Subject must be able to walk between 200 to 500 meters on the 6MWT
23. Upright FVC must be 30% to 80% of predicted normal value

Exclusion Criteria

23. Subject has received any ERT, including alglucosidase alfa at any time, or any investigational therapy for Pompe disease within 30 days or 5 half-lives of the therapy or treatment, whichever is longer, prior to the Baseline Visit, or anticipates doing so during the study
24. Subject has received treatment with prohibited medications within 30 days of the Baseline Visit
25. Subject, if female, is pregnant or breastfeeding at screening
26. Subject, whether male or female, is planning to conceive a child during the study
27. Subject requires invasive ventilatory support
28. Subject uses noninvasive ventilatory support \geq 6 hours a day while awake
29. Subject has a medical or any other extenuating condition or circumstance that may, in the opinion of the investigator or the Medical Monitor, pose an undue safety risk to the subject or compromise his/her ability to comply with protocol requirements
30. Subject has a history of allergy or sensitivity to miglustat or other iminosugars
31. Subjects with active systemic autoimmune disease such as lupus, scleroderma, or rheumatoid arthritis; all subjects with autoimmune disease must be discussed with the Amicus Medical Monitor
32. Subjects with active bronchial asthma; all subjects with bronchial asthma must be discussed with the Amicus Medical Monitor

Cohort 4**Inclusion Criteria**

24. Male and female subjects between 18 and 75 years of age, inclusive
25. Subject must provide signed informed consent prior to any study-related procedures
26. Subject has documented 6MWT on three separate occasions, each at least six months apart with at least two values in the past three years
27. Subjects of childbearing potential must agree to use medically accepted methods of contraception during the study and for 90 days after last co-administration of ATB200 and AT2221
28. Subject has a diagnosis of Pompe disease based on documented deficiency of GAA enzyme activity or by *GAA* genotyping
29. Subject has received ERT for the previous \geq 7 years
30. Subject is currently receiving alglucosidase alfa (Myozyme/Lumizyme) at a frequency of once every other week
31. Subject has received and completed the last 2 infusions without a drug-related AE resulting in dose interruption
32. Subject must be able to walk between 75 and 600 meters on the 6MWT
33. Upright FVC must be 30% to 85% of predicted normal value

Exclusion Criteria

33. Subject has received any investigational therapy including adjunctive therapy for Pompe disease, other than alglucosidase alfa within 30 days or 5 half-lives of the therapy or treatment, whichever is longer, prior to the Baseline Visit, or anticipates doing so during the study
34. Subject has received treatment with prohibited medications within 30 days of the Baseline Visit
35. Subject, if female, is pregnant or breastfeeding at screening
36. Subject, whether male or female, is planning to conceive a child during the study
37. Subject requires invasive ventilatory support
38. Subject uses noninvasive ventilatory support \geq 6 hours a day while awake
39. Subject has a medical or any other extenuating condition or circumstance that may, in the opinion of the investigator or the Medical Monitor, pose an undue safety risk to the subject or compromise his/her ability to comply with protocol requirements
40. Subject has a history of anaphylaxis to alglucosidase alfa
41. Subject has a history of high sustained anti-rhGAA antibodies
42. Subject has a history of allergy or sensitivity to miglustat or other iminosugars

43. Subjects with active systemic autoimmune disease such as lupus, scleroderma, or rheumatoid arthritis; all subjects with autoimmune disease must be discussed with the Amicus Medical Monitor

44. Subjects with active bronchial asthma; all subjects with bronchial asthma must be discussed with the Amicus Medical Monitor

Investigational Product, Dosage, and Mode of Administration:

Stage 1 (consists of 3 dosing periods 2 weeks apart for Cohort 1)

- Period 1: a single-dose IV infusion of 5 mg/kg ATB200
- Period 2: a single-dose IV infusion of 10 mg/kg ATB200 to all subjects who have completed Period 1
- Period 3: a single-dose IV infusion of 20 mg/kg ATB200 to all subjects who have completed Period 2

Stage 2 (consists of 2 dosing periods, each comprising 3 study treatment doses, 2 weeks apart for Cohort 1)

- Period 4: 130 mg of AT2221 will be administered orally 1 hour before a single-dose IV infusion of 20 mg/kg ATB200 to all subjects who have completed Period 3 (repeated every 2 weeks for a total of 3 administrations)
- Period 5: 260 mg of AT2221 will be administered orally 1 hour before a single-dose IV infusion of 20 mg/kg ATB200 to all subjects who have completed Period 4 (repeated every 2 weeks for a total of 3 administrations)

Stage 3 (consists of multiple study-dosing, administered every 2 weeks apart for a duration of 24 months)

Stage 4 (consists of multiple study-dosing, administered every 2 weeks apart until study treatment approval or discontinuation of the program)

Study treatment for all subjects in Stage 3 will consist of AT2221 administered orally at 260 mg followed approximately 1 hour later by a single-dose IV infusion of ATB200 at 20 mg/kg (repeated every 2 weeks for up to 24 months).

Note: Subjects are required to fast at least 2 hours before and 2 hours after administration of oral AT2221.

Total Duration of Study:

- Screening: up to 4 weeks
- Stage 1 + Stage 2: 18 weeks
- Stage 3: 24 months
- Stage 4: Until completion or drug approval

Criteria for Evaluation:**Primary:**

Safety assessments:

- PEs
- Vital signs, including body temperature, RR, HR, and BP
- AEs, including IARs
- 12-lead ECG
- Clinical safety laboratory assessments: serum chemistry, hematology, and urinalysis

PK of plasma ATB200 and AT2221:

- Plasma GAA activity levels and total GAA protein concentrations PK parameters: maximum observed plasma concentration (C_{max}), time to reach the maximum observed plasma concentration (t_{max}), area under the plasma-drug concentration time curve from Time 0 to the time of last measurable concentration (AUC_{0-t}), area under the plasma-drug concentration time curve from Time 0 extrapolated to infinity ($AUC_{0-\infty}$), alpha- and beta-phase half-life ($t_{1/2}$), total clearance following IV administration (CL_T), and steady state volume of distribution (V_{ss})
- Ratios of plasma GAA activity levels and total GAA protein concentration C_{max} , AUC_{0-t} , and $AUC_{0-\infty}$ for all dose regimens
- Plasma AT2221 PK parameters: C_{max} , t_{max} , AUC_{0-t} , $AUC_{0-\infty}$, and $t_{1/2}$, apparent total clearance of drug following oral administration (CL_T/F), and terminal phase volume of distribution following oral administration (V_z/F) for each dose level
- Ratio of plasma AT2221 PK parameters: C_{max} , AUC_{0-t} , and $AUC_{0-\infty}$ for each dose level
- Exposure estimates from sparse plasma total GAA protein concentrations after at least 18 months on ATB200/AT2221 treatment in Cohorts 1 and 3 patients will be compared to exposures after the first and third doses of 20 mg/kg ATB200 + 260 mg AT2221.

Functional Assessments (performed at Baseline and every 3 months in Stage 3):

For Ambulatory Subjects:

- Motor Function Tests
 - 6MWT
 - 10-Meter Walk Test (10MWT)
 - Gait, Stairs, Gower, and Chair maneuver (GSGC)
 - Timed Up and Go (TUG)

- Muscle Strength Test
 - medical research criteria (MRC) and hand-held dynamometer for both upper and lower limbs
- PFTs
 - FVC, maximum inspiratory pressure (MIP), maximum expiratory pressure (MEP), and Sniff Nasal Inspiratory Pressure (SNIP)

For Nonambulatory Subjects:

- Muscle Strength Test - Upper Limbs Only
 - MRC and hand-held dynamometer performed for upper limbs only
- PFTs - in subjects without invasive ventilatory support only
 - FVC, MIP, MEP, and SNIP

Patient-reported Outcomes (performed at Baseline and every 3 months in Stage 3):

- FSS
- RHS
- R-PAct Scale
- PROMIS instruments for dyspnea, fatigue, physical functioning, and upper extremity

Exploratory:

- Anti-rhGAA antibodies (total and neutralizing)
- Cross-reactivity of anti-rhGAA antibodies to alglucosidase alfa
- Pro-inflammatory cytokines and other biomarkers of immune system activation
- PD biomarkers: Hex4 and serum CK

Methods of Analysis:

Statistical Methods for PK Parameters:

Details of the analysis methods related to PK parameters will be provided in a stand-alone PK Statistical Analysis Plan (PK SAP). In general, basic descriptive statistics will be provided for all PK parameters.

Cohort 1

- Dose proportionality assessment on GAA activity levels and total GAA protein concentration exposure (C_{max} , AUC_{0-t} , and $AUC_{0-\infty}$) ratios of 5, 10, and 20 mg/kg ATB200 alone.
- Analysis of variance (ANOVA) on GAA activity levels and total GAA protein concentration exposure (C_{max} , AUC_{0-t} , and $AUC_{0-\infty}$) ratios of 20 mg/kg ATB200

alone versus 20 mg/kg ATB200 + 130 mg AT2221, and versus 20 mg/kg ATB200 + 260 mg AT2221.

- Dose proportionality assessment for exposure ratios (C_{max} , AUC_{0-t} , and $AUC_{0-\infty}$) between 130 mg and 260 mg AT2221.
- The effect of immunogenicity results on PK, PD, and safety will be evaluated. Further details will be provided in the Statistical Analysis Plan (SAP).

Cohort 3

- ANOVA on GAA activity levels and total GAA protein concentration exposure (C_{max} , AUC_{0-t} , and $AUC_{0-\infty}$) ratios of 20 mg/kg ATB200 + 260 mg AT2221 in subjects from Cohort 3 versus 20 mg/kg ATB200 alone in subjects from Cohort 1, versus 20 mg/kg ATB200 + 130 mg AT2221 in subjects from Cohort 1, and versus 20 mg/kg ATB200 + 260 mg AT2221 in subjects from Cohort 1.
- ANOVA on AT2221 exposure ratios (which will have the same PK parameters) for 260 mg AT2221 in subjects from Cohort 3 versus 130 mg AT2221 and 260 mg AT2221 in subjects from Cohort 1.

Statistical Methods for Non-PK-Specific Parameters:

Details of the analysis methods related to all non-PK-specific parameters will be provided in a separate SAP for the study.

In general, descriptive statistics (n, mean, standard deviation [SD], median, minimum, and maximum) will be provided for all efficacy continuous variables. Each cohort will have its own baseline, and analysis will be performed by cohort and overall. In addition, summary analyses will be performed by combining Cohort 1, 3, and 4 for ambulatory subjects, or by combining Cohort 1 and 4 for ERT-experienced subjects. For Cohort 1, the analysis will also be provided by treatment dosing regimen. The visit values and the change (and percent change) from baseline to the post-baseline assessment will be analyzed by scheduled visit. The 95% confidence interval for the mean (and percent mean) change from baseline by scheduled visit will be provided for summary purposes only. In addition, the visit values and derived values for each subject will be provided in data listings.

Safety and other variables that are continuous (including vital signs, laboratory assessments, and immunogenicity values) will similarly be analyzed using descriptive statistics. Shift tables will be generated for safety laboratory parameters.

Summary statistics will be provided for all variables that are not PK parameters.

Adverse events and other variables that are categorical will be summarized using counts and percentage. In addition, categorical variables (excluding AEs) will be summarized by scheduled visits.

Interim Analyses: Interim analyses will be performed during the study as needed. Details for the interim analysis will be included in the SAP.

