Upon study completion or subject discontinuation, subjects who are confirmed positive for anti-rhGAA antibodies will complete follow-up immunological testing as long as they have a positive result for up to 12 months after the last dose of study drug (ie, at 1-, 3-, 6-, 9-, and 12-months follow-up) or until they begin treatment with another ERT or investigational therapy. If anti-rhGAA antibodies are not confirmed positive at follow-up time points earlier than 6 months, no further testing is required.

Safety Monitoring

Safety will be monitored by the Amicus Medical Monitor and the investigators on a continuous basis and on a regular basis by a Safety Steering Committee (SSC). The details of the membership, meeting schedules, procedures, roles, and responsibilities of the SSC are detailed in the SSC Charter.

Subjects will be monitored in a hospital or infusion center for 48 hours from the start of each infusion during Stage 1 (ie, ERT dose-escalation stage). Since the target infusion duration in the study is 4 hours, all subjects will be closely monitored for the first 4 hours during their infusion and then observed in hospital for an additional 44 hours prior to discharge. Subjects will be admitted and dosed at either an infusion center or a hospital and thereafter hospitalized for the remainder of the observation period.

In Stages 2 and 3, all subjects will be monitored at a hospital or infusion center for an additional 2 to 4 hours from the end of their infusion. Once a subject has completed 1 year in Stage 3, the subjects who have not experienced IARs for the prior 6 months, can be monitored for 1 hour from the end of their infusion, at the PI's discretion. Subjects who switch to home infusion, must be monitored for 2 to 4 hours after the end of their infusions for a period of at least 3 months. If no IARs or other AEs occur during the 3 months, the monitoring can be reduced to 1 hour post infusion at the PIs discretion.

When at least 1 of the 2 Cohort 1 sentinel subjects has completed Stage 2, Period 5 sentinel dosing and the safety data has been reviewed by the SSC, subjects from Cohorts 2 and 3 can begin enrollment into Stage 3. The first 2 subjects from Cohorts 2 and 3 will undergo sentinel dosing in the same manner as subjects from Cohort 1 during Stage 2.

Sentinel Dosing

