8.2. Safety Monitoring and Sentinel Dosing

Safety will be monitored by the Amicus Medical Monitor and the investigators on a continuous basis and on a regular basis by a Safety Steering Committee (SSC). The details of the membership, meeting schedules, procedures, roles, and responsibilities of the SSC are detailed in the SSC Charter.

Study treatment may be interrupted or permanently stopped by the Amicus Medical Monitor and the SSC, if warranted by the safety and tolerability data. Subjects will be monitored in a hospital or infusion center for 48 hours from the start of each infusion during Stage 1 (ie, ERT dose-escalation stage). Since the target infusion duration in the study is 4 hours, all subjects will be closely monitored for the first 4 hours during their infusion and then observed in hospital for an additional 44 hours prior to discharge. Subjects will be admitted and dosed at either an infusion center or a hospital and thereafter hospitalized for the remainder of the observation period.

In Stages 2 and 3, all subjects will be monitored at a hospital or infusion center for an additional 2 to 4 hours from the end of their infusion. Once a subject has completed one year in Stage 3, the subjects, who have not experienced IARs for prior 6 months, can be monitored for one hour post infusion at the PI's discretion. Subjects who switch to home infusion, must be monitored for 2 to

4 hours for a period of at least 3 months. If no IARs occur, the monitoring can be reduced to one hour post infusion at the PIs discretion. Refer to Section [11.1.3](#) for further information on IARs, including their reporting and management.

When at least one of the 2 Cohort 1 sentinel subjects has completed Period 5 dosing, and the safety data has been reviewed by the SSC, subjects from Cohorts 2 and 3 can begin enrollment into Stage 3. The first 2 subjects from Cohorts 2 and 3 will undergo sentinel dosing in the same manner as subjects from Cohort 1 during Stage 2.

Sentinel Dosing

The first 2 subjects in Cohort 1 of this study will be the sentinel subjects for the study and will be the first 2 subjects dosed in each period of the study (Periods 1 to 5). The first 2 subjects dosed in each cohort will be the sentinel subjects for that cohort. In the event that a sentinel subject is prematurely withdrawn from the study, he/she will be replaced by another subject.

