11.1.3. Infusion-associated Reactions

An IAR is a disorder characterized by 1 or more adverse reaction(s) to the infusion of pharmacological or biological substances. These reactions are classified into 2 major subtypes, immediate and late, according to the time interval between the infusion and the onset of an infusion-related AE.

The reactions are divided into 5 severity grades as follows:

1. Mild (requires observation only); for example, transient flushing or rash
2. Moderate (minimal, usually oral, intervention suffices); for example, urticaria/myalgia/drug fever
3. Severe (vital organ involved yet not in a life-threatening manner; usually requires parenteral medication); for example, bronchospasm/angioedema/hypotension
4. Life-threatening (multisystem involvement of vital organs, urgent and critical care required); for example, systemic anaphylactic reaction
5. Death

Immediate-type IARs commonly involve 1 or more of the following systems: skin (urticaria and erythema), eyes (conjunctivitis), nasopharynx (rhinorrhea, rhinitis), bronchopulmonary tissues (wheezing, bronchospasm), and gastrointestinal tract (diarrhea, vomiting).

Late-type reactions first manifest more than 24 hours post infusion, usually 1 to 3 days post infusion. The most common symptoms of late-type infusion reactions are pruritic skin eruptions, fever, malaise, and polyarthralgia.

Any symptom or sign occurring during or within 2 hours of completion of the infusion should be reported as an immediate-type IAR and deemed drug-related AE, unless an alternative obvious explanation exists, eg, mechanical fall. Any symptom or sign occurring between 2 and 24 hours will be recorded as an IAR if it fits within the description of an IAR in the investigator's opinion. It would be reported as immediate-type IAR and deemed a drug-related AE.

Any symptom or sign occurring between 24 and 96 hours after completion of the infusion that, in the investigator's opinion, fits the clinical description of a symptom or sign associated with an IAR should be reported as a late-type IAR and deemed a drug-related AE.

A symptom or sign that occurs 24 hours or later and in the investigator's opinion is possibly, probably, or likely an IAR should be reported as such and deemed drug-related AE.

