Note: The list of IAR symptoms provided in [Table 19](#) is not comprehensive. It is meant to serve as a guideline to the investigators to report and manage IAR as AE. [Table 19](#) also provides a guideline for management of IARs and anaphylaxis (see also [Appendix 1](#)). It is at the investigator's discretion to follow the guidelines or implement treatment protocol that their center is accustomed to following.

In the event that a subject experiences an IAR, the subject should be premedicated for subsequent infusions with antihistamines, steroids, and/or acetaminophen. The premedications should be continued for a period of up to 1 year. Decision regarding discontinuation of premedications should occur only after discussion with Amicus Medical Monitor.

Table 19: Guidelines for Management of Immediate Infusion-associated Reactions

Severity	Symptoms (such as, but not restricted to)	Management Guidelines
Mild reaction	Flushing Nausea Mild headache Tachycardia (pulse < 100 bpm) Abdominal pain	
REDUCE INFUSION RATE BY 50%
 
Contact investigator.
 
Give oral antihistamine/acetaminophen/paracetamol and/or IV antihistamine.
 
Prepare emergency equipment for any subsequent study treatment escalation.
 
Subject must be observed at site or medical facility for 2-4 hours after resolution of the symptoms.
 
Record all details of times, concomitant medications, and infusion rates.
 
Draw IgE and total GAA sample 6 to 8 and 24 hours after the start of the infusion reaction (2 samples).
 
IF SYMPTOMS PERSIST:
 
STOP THE INFUSION
 
After 30 minutes, if subject has improved, increase to previous infusion rate on direction of investigator/designee.
 
If subject has not improved after 60 minutes, consult with investigator as to whether additional medications should be administered.
 
If subject reacts for second time after return to the prior infusion rate, reduce rate by 50% and contact investigator/designee.
 
IF IN DOUBT, STOP INFUSION

Table 19: Guidelines for Management of Immediate Infusion-associated Reactions (Continued)

Severity	Symptoms (such as, but not restricted to)	Management Guidelines

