10.3.3. Additional Analysis of IARs

10.3.3.1. Analysis by Onset Intervals

The onset intervals (in months), defined relative to the first dose of the 20 mg/kg ATB200 + 260 mg AT2221 study drug, will be: ≤ 6 , > 6 to ≤ 12 , > 12 to ≤ 18 , > 18 to ≤ 24 , and > 24 . For Cohort 1 subjects, the first dose of the 20 mg/kg ATB200 + 260 mg AT2221 study drug happened in Stage 2 Period 5.

The event rates and changes in intensity over time (over these intervals) will be summarized. This analysis will further describe the clinical characteristics of IARs, and it can help determine whether the IARs disappear over time or appear late.

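### Post-infusion observation may drop to 1 hour later in the study, inside the 2-hour default IAR window, so the later IAR rates in SAP 10.3.3.1 may be biased downward by an unknown, possibly zero, amount

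*Protocol*

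**What the plan says.** **Observation.** For Stages 2 and 3, the Protocol synopsis (Safety Monitoring) says that "all subjects will be monitored at a hospital or infusion center for an additional 2 to 4 hours from the end of their infusion". It then relaxes this. The starting point is given as "Once a subject has completed 1 year in Stage 3". From then on, "the subjects who have not experienced IARs for the prior 6 months, can be monitored for 1 hour from the end of their infusion", if the investigator so decides. For home infusions the 2 to 4 hours apply for at least 3 months, after which the synopsis says "If no IARs or other AEs occur during the 3 months, the monitoring can be reduced to 1 hour post infusion". Protocol 8.2 words the home condition differently: "If no IARs occur, the monitoring can be reduced to one hour post infusion at the PIs discretion".

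**Definition.** Protocol 11.1.3 says "Any symptom or sign occurring during or within 2 hours of completion of the infusion should be reported as an immediate-type IAR", with an exception where there is an obvious other explanation. Between 2 and 24 hours, and from 24 to 96 hours, an event is an IAR on the investigator's judgement. After an IAR, "the subject should be premedicated for subsequent infusions with antihistamines, steroids, and/or acetaminophen", for up to a year.

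**Capture.** Adverse events are collected at every visit, including the two-weekly infusion-only visits (Protocol 10.5, 11.4). An IAR is an investigator's mark on any adverse event (SAP 10.3.2).

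**Analysis.** SAP 10.3.3.1 summarises IAR event rates and intensity for onset at ≤6, >6–12, >12–18, >18–24 and >24 months from the first 20 mg/kg + 260 mg dose. Its stated use is that "it can help determine whether the IARs disappear over time or appear late". SAP 10.3.3.3 groups IARs by time after infusion, and its first bin runs from 0 to under 2 hours. The SAP's IAR sections (10.3.2 to 10.3.3.3) neither adjust for observation length or infusion setting nor carry a caveat about them.

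**The concern.** A trend in event rates over time is interpretable only if events are looked for in the same way throughout. Here the permitted observation time changes during follow-up, and the shorter time lies inside the window that makes a sign an IAR by default.

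The subjects who may be watched for less time are those recently free of IARs, in whom a newly appearing reaction would arise. A missed event also leaves its subject recorded as IAR-free, so short observation can continue. The events most easily lost are mild ones such as flushing, and signs such as tachycardia or tachypnea that staff detect. The intensity trend is therefore exposed as well as the rate. At stake is the description of whether IARs wane with long-term treatment.

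**Working it through.** The documents give no figure for this effect, so there is none to reproduce.

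**1. Hours watched.** The infusion lasts about 4 h (Protocol 13.3.1).
- Full observation: 4 + 2 = 6 h to 4 + 4 = 8 h. Reduced: 4 + 1 = 5 h.
- Loss of staff-observed time: 1 − 5/6 = 17% to 1 − 5/8 = 37.5%.
- Of the default IAR window (4 + 2 = 6 h), 1/6 = 17% becomes unwatched. Of its 2 h post-infusion part, 1/2 = 50%.

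**2. Which intervals are affected** (30.4 days per month, as in SAP 10.2).
- Site infusions, one year in Stage 3. Cohorts 2–4: target day 361 (SAP Tables 5 and 6), 361/30.4 = 11.9 months. Cohort 1: relative day 403 (SAP Table 4), 403/30.4 = 13.3 months.
- Home infusions, Cohorts 2–4: 6 + 3 = 9 months under the 6-month rule (synopsis, Home Infusion), or 12 + 3 = 15 months under the one-year criterion in Protocol 10.6. For Cohort 1, counting treatment from Visit 6 (Day 43, 42 days before Visit 9), each is 42/30.4 = 1.4 months earlier.
- The Protocol's change summary dates the 6-month rule to Amendment 8 (10 January 2019). The 20 subjects in the August 2017 data cut (Protocol 6.4.2.6) were already more than 16 months past first dose by then. Month 9 could matter only for later enrollees, chiefly Cohort 4.

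The intervals beyond 12 months are therefore the ones mainly affected.

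**3. Size.** Assume a constant true rate and that every later infusion is watched for 1 h only. Let f be the share of IARs starting in the time no longer watched, and r the share of those still reported later. The apparent late/early ratio is R = 1 − f(1 − r). Neither f nor r is in the documents.

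| Assumed onset | f | r = 0 | r = 0.5 | r = 0.8 | r = 1 |
|---|---|---|---|---|---|
| Uniform over 4 h infusion + 2 h | 1/6 | 0.83 | 0.92 | 0.97 | 1.00 |
| Half start in the 2 h after infusion | 0.25 | 0.75 | 0.88 | 0.95 | 1.00 |
| All start in the 2 h after infusion | 0.50 | 0.50 | 0.75 | 0.90 | 1.00 |

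If only half of later infusions are watched for less time, the loss halves: for f = 1/6 and r = 0, R = 1 − 0.5 × 1/6 = 0.92.

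**4. Chance alone.** The interim data show 3 IARs in 400+ infusions, so at most 3/400 = 0.0075 per infusion. Taking 20 subjects and 13 infusions each per 6 months gives 260 infusions and 260 × 0.0075 = 1.95 expected IARs. With independent infusions, the probability of none is (1 − 0.0075)^260 = 0.14. With f = 1/6 and r = 0 it is (1 − 0.0075 × 5/6)^260 = 0.20. With f = 0.5 and r = 0 it is (1 − 0.0075 × 0.5)^260 = 0.38.

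**The case against.** The strongest reply is that unwatched does not mean unrecorded. Subjects are asked about adverse events every two weeks, an IAR can start up to 96 hours after infusion, and from Stage 2 on everything beyond 2 to 4 hours already depends on later reporting. An event at 1 to 2 hours is lost only if the subject does not report it or only staff could have detected it. This stands, and it is why the bias may be zero. It does not make recall equivalent to observation for mild or staff-detected signs.

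The reduction is also discretionary and closed to recent reactors. The 3 interim IARs came from 2 of 20 subjects. If IARs cluster in reactors, fewer events are exposed than the table in the working assumes. This stands too.

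A reader might infer that the SAP treats a fall as proof that IARs disappear. It does not. It states a two-directional descriptive purpose, and no inferential statistics are planned (SAP 6.2.1).

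Premedication might seem a second reason to expect a spurious decline. It is not an observation artefact. It runs for up to a year after an IAR, so its lapse could push later rates up. SAP 10.3.2 already lists it for each subject with an IAR, and SAP 7.8 summarises its use.

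**Conclusion.** The point holds as a possible downward ascertainment bias in the later intervals of SAP 10.3.3.1, chiefly beyond 12 months. The planned time-after-infusion bins cannot reveal it, because the first and second hours are pooled.

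Its size is unknown and may be nil. A ratio of 0.50 needs every IAR to start after the infusion, no later reporting, and 1-hour observation at every later infusion. The documents support none of these.

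Two stronger readings are tempting. One is that IARs could appear to vanish only because observation shrank. That would need nearly all IARs to start in the dropped time and go unreported, and sparse counts are a likelier cause of an empty interval. The other is that observation falls for everyone from month 9. The protocol makes the reduction optional and restricted, and the month-9 date depends on one of two conflicting home-infusion rules.

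This is an inexpensive improvement to a descriptive analysis.

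**What to change.** - **SAP 10.3.3.1:** keep the planned table. Add a sensitivity version limited to IARs with onset during the infusion or within 1 hour of its end, per infusion given, by the same onset intervals. That window is watched under every observation schedule in the synopsis and Protocol 8.2.
- **SAP 10.3.3.3:** split the first bin into 0 to <1 hour and 1 to <2 hours.
- **SAP 10.3.3.1 footnote:** state that permitted observation time, infusion setting and premedication use changed over the study.
- **No split of rates by premedication.** Protocol premedication follows an IAR, so the split is confounded by indication, and at about 2 expected IARs per interval the cells would be nearly empty.

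The cost is one extra table and one extra bin, using onset times that SAP 10.3.3.3 already needs. The drawback is smaller counts per interval. Protocol 11.4 asks only for best efforts on event times, so IARs without a usable onset time should be counted separately.

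Two protocol discrepancies must also be reconciled. The synopsis and 8.2 differ on the condition for shortening home observation (IARs or other adverse events, against IARs only). The synopsis and the opening of 10.6 give 6 months of treatment before home infusion, while the criteria list in 10.6 gives one year.
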